## **2. BACKGROUND AND SIGNIFICANCE**

### **2.1. Inflammatory signaling appears to be a key component of alcohol use disorder.**

Molecular and behavioral studies suggest a central role for the innate immune system in mediating the acute and chronic effects of alcohol and generally support an inflammatory hypothesis of alcohol use disorder. Neurotrophins, including glial (GDNF) and brain derived neurotrophic factor (BDNF), are essential for synaptic plasticity, neuron survival, and basic cell signaling, including midbrain dopamine transmission. In rodent models of AUD, reductions in GDNF and BDNF expression underlie dysfunctional striatal dopamine signaling, increased motivation to consume alcohol, and heightened alcohol reward. Conversely, increases in GDNF and BDNF signaling restores mesolimbic dopamine function, reduces alcohol self-administration, and attenuates relapse to alcohol seeking. In preclinical studies, induction of inflammation produces prolonged increases in alcohol consumption, and knocking out inflammatory signaling genes attenuates alcohol preference and self-administration.

Proinflammatory signaling also mediates acute alcohol-induced motor impairment, and chronic alcohol exposure produces long-lasting increases in systemic inflammation, which in turn is associated with sustained cognitive and behavioral impairment and brain damage. Furthermore, inflammation is thought to increase vulnerability to stress-induced drug seeking and relapse.

It is hypothesized that chronic alcohol consumption produces a sustained inflammatory state, and in turn, this alcohol-induced neuroinflammation contributes to the behavioral and neurotoxic effects of alcohol. Individuals with AUD are thought to have increased neuroinflammation throughout the brain, and elevated peripheral levels of proinflammatory cytokines have been

proposed as a biomarker for AUD. Nevertheless, there are contrasting findings such that a recent imaging study reported that individuals with AUD exhibit less activated microglia in the brain and blunted peripheral proinflammatory response than controls. In sum, the role of inflammation in AUD remains opaque, particularly in human/clinical studies.

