### 3. STUDY OBJECTIVES

#### 3.1. Primary Aims

Primary Aim #1: To test whether low dose endotoxin (0.8 ng/kg of body weight) will increase cue-induced craving for alcohol in non-treatment-seeking heavy drinkers, as compared to placebo and as compared to light drinking controls. Based on the correlational findings of a positive association between proinflammatory cytokines and alcohol craving (8, 9), as well as preclinical studies (16-18), we hypothesize that endotoxin will produce greater cue-induced alcohol craving than placebo infusion.

Primary Aim #2: To test whether low dose endotoxin (0.8 ng/kg of body weight) will increase depressed mood as compared to placebo. Based on recent work by our Co-Is (13), we hypothesize that endotoxin will produce greater increases in depressed mood than placebo infusion.

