### **8.1. Statistical Power**

A power analysis was conducted for the study based on results from a previous human endotoxin challenge carried out in a control sample by our collaborators ([name] et al., 2010). Effect size was calculated based on [name] et al.'s reported sample size of  $N = 39$  and  $F$ -statistic of 8.13 for increase in negative mood at T2 after endotoxin infusion, yielding Cohen's  $d = 0.4687$ . Power analysis was conducted according to Cohen's guidelines to determine the sample size needed to achieve a power  $\geq 0.80$  (i.e. 80%) at an alpha level of .05. Using the program G\*Power version 3.1 and selecting the repeated measures ANOVA, within-between interactions design, where alpha = .05, effect size  $f = 0.234$ , we arrived at a total  $N = 76$  completers (38 heavy drinkers and 38 healthy controls). Specifically, we powered the study

to detect differences from baseline to peak (T2) inflammatory response, given that the remaining data points post-peak tend to be similar and may obscure the effects of the inflammatory challenge. Individuals who experience severe sickness symptoms will be excluded (expected to be <5% of the sample).

**8.2. Aim 1: To test that low dose endotoxin will increase cue-induced craving for alcohol in heavy drinkers as compared to light drinking controls, and as compared to placebo.**

Repeated measures analyses of variance (ANOVAs) will be conducted using PROC GLM in SAS Statistical Software. Specifically, in the repeated measures ANOVA models, Group (Heavy drinking versus light drinking) will be a two level between-subjects factor, Treatment (endotoxin vs. placebo) will be a two level between-subjects factor, and Cue (water cues versus alcohol cues) will be a between-subjects factor. The dependent measure will be self-reported alcohol craving captured by the Alcohol Craving Questionnaire. Sickness symptoms and drinking history (i.e., drinks per day and drinks per drinking day in past year) will be used as covariates in these analyses.

**8.3. Aim 2: To test whether low dose endotoxin (0.8 ng/kg of body weight) will increase depressed mood as compared to placebo.**

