Repeated measures ANOVAs in which Group (Heavy drinking versus light drinking) will be a two level between-subjects factor, and Treatment (endotoxin vs. placebo) is a two level between-subjects factor. The outcome measure is depressed mood (captured by the POMS). Sickness symptoms and drinking history will also be included as covariates in these analyses.

**8.4. Exploratory Analysis: To test associations between plasma levels of proinflammatory cytokines (IL-6 and TNF- $\alpha$ ), depressed mood, and alcohol craving during the challenge; and examine sex differences in responses to the endotoxin challenge.**

Repeated measures ANOVAs will be used to capture the effects of Treatment (endotoxin vs. placebo) by Time (T0 to T2) for the proposed planned outcomes (i.e. proinflammatory cytokines, hourly craving scores) as well as models that include sex as a between-subjects factor. As with the primary aims, sickness symptoms and drinking history will be entered in these models as covariates.

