**8.5. Exploratory Analysis: To test the effect of low dose endotoxin on neural alcohol cue-reactivity**

fMRI Data Processing: FSL 6.0 ([www.fmrib.ox.ac.uk/fsl](http://www.fmrib.ox.ac.uk/fsl)) will be used for the neuroimaging analyses. Motion correction will be carried out using the Motion Correction Linear Image Registration Tool (McFLIRT, Version 5.0) with the estimated motion parameters entered as covariates in the general linear model. Brain Extraction Tool (BET) will be used for non-brain tissue/skull removal. The images will be smoothed using a FWHM Gaussian kernel (5 mm) and high-pass filtered (100s cutoff) in the temporal domain with the FMRI Expert Analysis Tool (FEAT, Version 6.0). The EPI images will first be registered to the MBW, then to the MPRAGE using affine linear transformations, and into standard MNI space. Registration to standard space will be refined by FSL's FNIRT nonlinear registration.

**fMRI Data Analysis:** Explanatory variables for the alcohol cues task will be created by convolving delta functions representing the onset of experimental events (alcohol, non-alcohol, blurred, and fixation cues; 24-s duration) with a double-gamma hemodynamic response function in FEAT. Temporal derivatives will be included as covariates. A 2X2 ANOVA in which Group (heavy drinker versus light drinker) will be a two level between-subjects factor and Treatment (endotoxin vs. placebo) is a two level between-subjects factor. The main contrast of interest will be activation during alcohol vs. non-alcohol blocks (ALC vs. BEV). Z-statistic images will be thresholded with cluster-based corrections for multiple comparisons based on the theory of Gaussian Random Fields with a cluster-forming threshold of  $Z>3.1$  and a cluster-probability threshold of  $p<0.05$ . Sickness symptoms will also be included as covariates in these analyses.

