## **8.6. Exploratory Analysis: To determine the effect of low dose on reward responsiveness**

Repeated measures ANOVAs in which Group (Heavy drinking versus light drinking) will be a two level between-subjects factor, and Treatment (endotoxin vs. placebo) is a two level between-subjects factor. The outcome measure is reward responsiveness (captured by the Probabilistic Reward Task and Reward Responsiveness Scale). Sickness symptoms and drinking history will also be included as covariates in these analyses.

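### The cytokine model in section 8.4 omits drinker group, so the plan does not test whether heavy and light drinkers mount the same IL-6 and TNF-alpha response to endotoxin

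*Combined protocol and SAP*

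**What the plan says.** For the cytokines and the hourly craving scores, section 8.4 states: "Repeated measures ANOVAs will be used to capture the effects of Treatment (endotoxin vs. placebo) by Time (T0 to T2"), "as well as models that include sex as a between-subjects factor". It adds that "sickness symptoms and drinking history will be entered in these models as covariates". No drinker-group factor is named.

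The other outcome models do name it:
- 8.2 (craving): "Group (Heavy drinking versus light drinking) will be a two level between-subjects factor, Treatment (endotoxin vs. placebo) will be a two level between-subjects factor".
- 8.3 (depressed mood): the same two between-subjects factors.
- 8.5 (fMRI): "Group (heavy drinker versus light drinker) will be a two level between-subjects factor".
- 8.6 (reward responsiveness): "Repeated measures ANOVAs in which Group (Heavy drinking versus light drinking) will be a two level between-subjects factor".

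Primary Aim 1 in section 3.1 asks about craving in heavy drinkers "as compared to placebo and as compared to light drinking controls". Section 2.1 describes raised inflammation in AUD and then, as a contrasting finding, an imaging study in which "individuals with AUD exhibit less activated microglia in the brain and blunted peripheral proinflammatory response than controls". Sections 4.1, 5.4.4 and 6.2.15 plan blood sampling at baseline and hourly to four hours, with no restriction by drinker group.

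**The concern.** Treatment is randomised; drinker group is not. Both groups receive the same weight-based challenge, but that does not guarantee the same cytokine rise. If the rise differs, a heavy-versus-light difference in the endotoxin effect on craving mixes two things: how large the inflammatory response was, and how strongly craving follows it. Greater sensitivity in heavy drinkers could be masked by a smaller cytokine response, or a difference in cytokine response could look like a difference in sensitivity.

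The model in 8.4 averages the response over both groups. A clear average rise could come mainly from light drinkers, and the plan would not show how well the challenge worked in the heavy drinkers, who are the population of interest. Drinking history as a covariate does not repair this. With no stated interaction with Treatment, it does not let the endotoxin effect differ by group.

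**Working it through.** **1. Which models name Group.**

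| Section | Outcome | Group named? |
|---|---|---|
| 8.2 | cue-induced craving | yes |
| 8.3 | depressed mood | yes |
| 8.4 | IL-6, TNF-alpha, hourly craving | no (Treatment, Time, sex) |
| 8.5 | fMRI cue reactivity | yes |
| 8.6 | reward responsiveness | yes |

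No other section plans a heavy-versus-light comparison of cytokines.

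**2. The plan's own figure.** Section 8.1 gives F = 8.13 with N = 39, d = 0.4687, f = 0.234 and 76 completers. √(8.13/37) = 0.4688, and half of that is 0.234. For a within-between interaction with 2 groups, 2 times and an assumed zero correlation, λ = f² × N × 2. At N = 76, λ = 0.234² × 76 × 2 = 8.32 and power is 0.813; the smallest N reaching 0.80 is 74. So 76 reproduces to within two participants. That calculation does not address a cytokine comparison by group. It is used below only for the cell size.

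**3. Cell size.** 38 heavy and 38 light completers (8.1). The allocation ratio is not stated, and drinker group is not among the urn factors in 5.4.1. Assuming 1:1 within each group: 38/2 = 19 per cell.

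**4. Precision and power**, in SD units of the T0-to-T2 change in log cytokine, two-sided 0.05, no covariates.
- Heavy minus light, endotoxin only: SE = √(2/19) = 0.324 SD. Half-width = 2.028 × 0.324 = 0.66 SD (36 df).
- Group × Treatment × Time: SE = √(4/19) = 0.459 SD. Half-width = 1.993 × 0.459 = 0.91 SD (72 df).
- 80% power by noncentral t: about 0.93 SD and about 1.30 SD respectively.
- The half-width is not a detectable effect: a true endotoxin-only difference of 0.66 SD has power of about 0.51.

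**5. As percentage blunting**, 1 − exp(−D × SD), at an assumed log SD of 0.6 to 0.8 (the documents give none).

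| Contrast | D | log SD 0.6 | log SD 0.8 |
|---|---|---|---|
| Endotoxin only | 0.93 | 1 − exp(−0.558) = 43% | 1 − exp(−0.744) = 52% |
| Interaction | 1.30 | 1 − exp(−0.78) = 54% | 1 − exp(−1.04) = 65% |

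For an assumed 30% blunting, −ln(0.7) = 0.357, which is 0.59 SD at log SD 0.6 and 0.45 SD at 0.8. Power is 43% and 27% for the endotoxin-only contrast, and 25% and 16% for the interaction.

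**6. What pooling can hide (illustration only).** Assume a cytokine rise of 2 SD in light and 1 SD in heavy drinkers, and the same craving slope of 0.5 in both, so there is no difference in sensitivity. The craving Group × Treatment effect is then 0.5 × (1 − 2) = −0.50. In simulation with 19 per cell, its rejection rate is 0.16, against 0.05 when the rises are equal. The pooled model shows a rise of (2 + 1)/2 = 1.5 SD and no sign of the split. A Group × Treatment term on cytokine change would detect it with power of about 0.58.

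**The case against.** The case against has several parts.

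- **The data will exist.** A reader might infer that the trial cannot separate inflammatory response from sensitivity. The documents do not support that: cytokines are sampled in both groups, so what is missing is a prespecified comparison. This stands, and it limits the point.
- **Aim 1's stated hypothesis is endotoxin against placebo.** That contrast is randomised and does not need equal cytokine responses across drinker groups. This also stands. But the aim, and the title of 8.2, also name the comparison with light drinkers, and that comparison is the one affected.
- **8.4 matches its aims.** Exploratory Aims 1 and 2 concern associations and sex differences, not drinker-group differences in cytokines. True; the need for the comparison comes from how Aim 1 will be read.
- **The evidence of blunting is contested and concerns AUD.** Section 2.1 sets it beside evidence of raised cytokines. Heavy drinkers here qualify by an AUDIT score of 8 to 15 and a recent binge (5.2.1), and an AUD diagnosis is not required. A reader might infer that blunting should be expected in this sample; the documents do not show that. They show the direction is uncertain, which is a reason to estimate it.
- **Power is low.** Moderate blunting would usually be missed by a significance test. This stands, and is why the remedy rests on an estimate with an interval.

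**Conclusion.** The point holds as a gap in the prespecified exploratory analysis. Section 8.4 is the only outcome model in section 8 without drinker Group, and its covariates do not replace a Group × Treatment × Time term. As written, the heavy-versus-light part of Aim 1 would be read with no planned check of cytokine response by group.

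The comparison would be informative only for large differences: roughly 43% to 52% blunting for 80% power within the endotoxin arm, and 54% to 65% for the interaction. These figures assume 19 per cell, log SDs of 0.6 to 0.8 and no covariates. The randomised endotoxin-placebo contrast within heavy drinkers is not undermined.

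A reader might also infer that adding Group to the cytokine model would by itself settle whether a craving difference reflects sensitivity. It would not. It shows whether the responses differ; attribution also needs craving modelled on cytokines by group. Section 8.4 is titled as testing associations but specifies no such model.

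**What to change.** In section 8.4, before unblinding:

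1. Add Group and its interactions, up to Group × Treatment × Time (T0 to T2), to the IL-6 and TNF-alpha models.
2. Report the endotoxin effect on log cytokine change within each drinker group, and the heavy-minus-light difference, each with a 95% CI.
3. Make this comparison without the drinking-history covariates, which closely track how Group is defined, and without any post-infusion sickness score, which endotoxin can itself affect. Section 8.4 does not say at which time point the sickness score is taken.
4. Add an exploratory model of craving change on cytokine change by Group.
5. State that a heavy-versus-light craving difference will be read alongside these estimates, and that a non-significant cytokine interaction is not evidence of equal response.

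The cost is SAP wording and a few error degrees of freedom, with no new samples, assays or participants. The drawback is low power for moderate differences, so the output is an estimate with a wide interval.

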**8.5. Exploratory Analysis: To test the effect of low dose endotoxin on neural alcohol cue-reactivity**

fMRI Data Processing: FSL 6.0 ([www.fmrib.ox.ac.uk/fsl](http://www.fmrib.ox.ac.uk/fsl)) will be used for the neuroimaging analyses. Motion correction will be carried out using the Motion Correction Linear Image Registration Tool (McFLIRT, Version 5.0) with the estimated motion parameters entered as covariates in the general linear model. Brain Extraction Tool (BET) will be used for non-brain tissue/skull removal. The images will be smoothed using a FWHM Gaussian kernel (5 mm) and high-pass filtered (100s cutoff) in the temporal domain with the FMRI Expert Analysis Tool (FEAT, Version 6.0). The EPI images will first be registered to the MBW, then to the MPRAGE using affine linear transformations, and into standard MNI space. Registration to standard space will be refined by FSL's FNIRT nonlinear registration.

**fMRI Data Analysis:** Explanatory variables for the alcohol cues task will be created by convolving delta functions representing the onset of experimental events (alcohol, non-alcohol, blurred, and fixation cues; 24-s duration) with a double-gamma hemodynamic response function in FEAT. Temporal derivatives will be included as covariates. A 2X2 ANOVA in which Group (heavy drinker versus light drinker) will be a two level between-subjects factor and Treatment (endotoxin vs. placebo) is a two level between-subjects factor. The main contrast of interest will be activation during alcohol vs. non-alcohol blocks (ALC vs. BEV). Z-statistic images will be thresholded with cluster-based corrections for multiple comparisons based on the theory of Gaussian Random Fields with a cluster-forming threshold of  $Z>3.1$  and a cluster-probability threshold of  $p<0.05$ . Sickness symptoms will also be included as covariates in these analyses.

## **8.6. Exploratory Analysis: To determine the effect of low dose on reward responsiveness**

Repeated measures ANOVAs in which Group (Heavy drinking versus light drinking) will be a two level between-subjects factor, and Treatment (endotoxin vs. placebo) is a two level between-subjects factor. The outcome measure is reward responsiveness (captured by the Probabilistic Reward Task and Reward Responsiveness Scale). Sickness symptoms and drinking history will also be included as covariates in these analyses.

# **9. ETHICS**

## **9.1. IRB Review**

The study will be conducted under a protocol reviewed by the UCLA IRB; the study is to be conducted by scientifically and medically qualified persons; the benefits of the study are in proportion to the risks; the rights and welfare of the subjects will be respected; the physicians conducting the study will ensure that the hazards do not outweigh the potential benefits; the results to be reported will be accurate; subjects will give their informed consent and will be competent to do so and not under duress; and all study staff will comply with the ethical principles in 21 Code of Federal Regulations (CFR) Part 50 and the Belmont Principles.

### **9.1.1. Protocol Modifications**

All necessary protocol changes will be submitted in writing as protocol amendments to the IRB by the PI for approval prior to implementation.

### **9.1.2. Protocol Deviation Reporting Procedures**

All subject-specific deviations from the protocol are to be documented. The PI or designee will be responsible for identifying and reporting all deviations, which are occurrences involving a procedure that did not follow the study protocol. Any protocol deviation that adversely affects the safety or rights of a subject or scientific integrity of the study is considered a major deviation and will be reported immediately to the UCLA IRB.

## **9.2. Ethical Conduct of the Study**

This study will be conducted in accordance with all applicable Federal human research protections requirements and the Belmont Principles of respect for persons, beneficence, and justice. The procedures set out in this study are designed to ensure that all study personnel

abide by the principles of the ICH GCP Guideline and the Code of Federal Regulations (CFR). The PI confirms this by signing FDA Form 1572.

#### 9.2.1. Confidentiality of Data and Subject Records

To maintain subject confidentiality, all laboratory specimens, eCRFs, reports and other records will be identified by a subject number only. Research and clinical records will be stored in a locked cabinet. Only research staff, and other required regulatory representatives will have access to the records. Subject information will not be released without written permission. The PI has received a Certificate of Confidentiality for this study.

#### 9.2.2. Compensation for Participation

Subjects will be compensated for travel expenses and for time contributed to this research study in the form of cash. Compensation will be provided at each subject visit and is detailed in the informed consent form.

#### 9.2.3. Written Informed Consent

The informed consent process and document will be reviewed and approved by the IRB and prior to initiation of the study. The consent document contains a full explanation of the possible risks, advantages, and alternate treatment options, and availability of treatment in the case of injury, in accordance with 21 CFR Part 50. The consent document indicates that by signature, the subject, permits access to relevant medical records as described above. A written informed consent document, in compliance with 21 CFR Part 50, 32 CFR Part 219, and the Belmont Principles, and HIPAA Authorization will be signed by the subject before any study-related procedures are initiated for each subject. All potential subjects for the study will be given a current copy of the Informed Consent Form to read. All aspects of the study and informed consent will be explained in lay language to the subject by either the investigator, or a medically trained designee. Any subject who is unable to demonstrate understanding of the information contained in the informed consent will be excluded from study participation.

All study subjects will be given a copy of the signed informed consent.

#### 9.2.4. Delegation of Responsibilities and Adequate Resources

The PI should have adequate time to conduct the study properly and should have an adequate number of qualified staff to assist with the conduct of the study. The term “investigator” used throughout this protocol refers to the PI and/or qualified Sub-investigators. The PI may delegate responsibilities to other study site personnel. The PI shall delegate tasks only to individuals qualified by education, training, and experience to perform the delegated tasks. The PI shall have direct oversight of all delegated activities and shall document delegation of responsibilities. The PI is responsible for ensuring all delegated staff has been properly trained on the protocol and their assigned study responsibilities. A delegation log identifying all delegated duties and the individual to whom they have been delegated will be maintained at the study site.

